14.3 SERIOUS ADVERSE EVENT

As per ICH-GCP (E6, step 5) guidelines, serious adverse event (SAE) or serious adverse drug reaction is any medical occurrence that at any dose:

No.	Description
1	Results in death
2	Is life threatening: refers to immediate risk of death as the event occurred per the reporter. A life-threatening event does not include an event that, had it occurred in a more severe form, might have caused death but, as it actually occurred, did not create an immediate risk of death. For example, hepatitis that resolved without evidence of hepatic failure would not be considered life-threatening, even though hepatitis of a more severe nature can be fatal. Similarly, an allergic reaction resulting in angioedema of the face would not be life-threatening, even though angioedema of the larynx, allergic bronchospasm, or anaphylaxis can be fatal.
3	Requires inpatient hospitalization or prolongation of existing hospitalization*
4	Results in persistent or significant disability/incapacity: is defined as a substantial disruption in a person's ability to conduct normal life functions
5	is a congenital anomaly or birth defect
6	Is an important medical event: A medical event that may not result in death, be life-threatening, or require hospitalization may be considered SAEs when, based on appropriate medical judgment, they may jeopardize the subject and may require medical or surgical intervention to prevent one of the outcomes listed in this definition. Examples of such medical events include allergic bronchospasm requiring intensive treatment in an emergency room or at home, blood dyscrasias or convulsions that do not result in hospitalization, or development of drug dependency or drug abuse.

* Examples of situations which do not fulfill this criterion in the absence of an AE include, but are not limited to, are as follows:

- A hospitalization or prolongation of hospitalization is needed for a procedure required by the protocol
- Hospitalization or prolongation of hospitalization is part of a routine procedure followed by the site (e.g., stent removal after surgery). This should be recorded in the study file

Spectranetics Corporation

Study Protocol Number: ELCA-1016

Version 1.0

Dated: 12 Oct 2016

- A hospitalization for a pre-existing condition that has not worsened
- Hospitalization for social reasons

All SAEs will be recorded on the appropriate SAE form, followed through resolution by the study investigator and must be reviewed and evaluated by a study investigator.

14.4 ABNORMAL LABORATORY VALUES OR ABNORMAL CLINICAL FINDINGS

Collection of laboratory data should be limited to those laboratory parameters that are relevant to safety, study outcome measures, and/or clinical outcome. Investigator or designee will record and report only those abnormal laboratory values, which are clinically significant considering the change from the baseline value.

14.5 SEVERITY OF AN ADVERSE EVENT

For evaluating severity of an AE / SAE, following classification will be used to quantify intensity as per the clinical judgment of the investigator:

- Mild: The event is transient and easily tolerated by the subject. Does not generally warrant medical intervention;
- Moderate: The event causes the subject discomfort and interrupts the subject's usual activities. May warrant medical intervention; or
- Severe: The event usually incapacitating and causes considerable interference with the subject's usual activities. Warrants systemic drug therapy or other treatment. Changes in the severity of an AE should be documented to allow an assessment of the duration of the event at each level of intensity to be performed. Adverse events characterized as intermittent require documentation of onset and duration of each episode.

14.6 CAUSAL RELATIONSHIP OF ADVERSE EVENT

The investigator should use his medical judgment to determine the relationship, considering all relevant factors, including pattern of reaction, temporal relationship, de-challenge or re-challenge, confounding factors such as concomitant medication, concomitant diseases and relevant history. Assessment of causal relationship should be recorded in the eCRFs and in SAE form (in case of SAEs).

Spectranetics Corporation

Study Protocol Number: ELCA-1016

Version 1.0

Dated: 12 Oct 2016

The investigator will use the following definitions to assess the relationship of the adverse event to the use of study drug:

No.	Description
1	Unrelated : The Adverse Event is clearly not related to the investigational agent, disease, concomitant medication, or other contributing cause.
2	Unlikely : The Adverse Event is doubtfully related to the investigational agent, disease, concomitant medication, or other contributing cause.
3	Possible : The Adverse Event may be related to the investigational agent, disease, concomitant medication, or other contributing cause.
4	Probable : The Adverse Event is likely related to the investigational agent, disease, concomitant medication, or other contributing cause.
5	Definite : The Adverse Event is clearly related to the investigational agent, disease, concomitant medication, or other contributing cause.

For causality assessments, events meeting the categories of probable or possible will be considered "related." Events that are reported as unlikely will be considered "not related."

If an investigator's opinion of possible, probable, or unrelated to study drug is given, another cause of event must be provided by the investigator for the serious adverse event.

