12.5 STUDY ENDPOINTS

Efficacy Endpoint:

- Device Success: Successful crossing of the ELCA Catheter across the entire length of the stenotic lesion
- Procedural Success: Target lesions with less than 50% residual stenosis after laser and adjunctive therapy

Safety Endpoint:

- Freedom from major adverse cardiac events (MACE) through hospital discharge and at one month
MACE is defined as Death, Non-Q-wave and Q-wave myocardial infarction (MI), Target Lesion Revascularization, Cardiac Tamponade and Life-threatening arrhythmias
- TIMI Flow
- Lesion Morphology
- Device-related complications
- Procedure-related complications

In order to fully characterize the procedure, information of all treated lesions will be collected irrespective of whether the lesion has been treated with ELCA[®] product.

Electronic Case Report Forms will be utilized to collect relevant information.

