16.3 SOURCE DATA

Original or signed and dated copies of all clinical findings, observations, and other activities throughout the clinical investigation must be recorded and maintained in the medical file of each enrolled subject. For data documented in the CRF respective source data in the medical record (source document) must be available.

The medical record/subjects record (source document) must contain, but is not limited to:

- Executed informed consent
- Subjects participation in the clinical investigation
- Demographics
- Documentation of medical history
- Intervention report
- Vessel and lesion sizes and characteristics
- All angiographies, ECGs, laboratory examination outcomes including reference values
- Discharge letter
- All adverse events: diagnosis, symptoms, onset date, severity, device and procedure relationship, action taken, outcome
- Concomitant medication
- Follow-up information
- Date of clinical investigation completion

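### Section 14.6 rates causality against one target, the study drug, although device-related and procedure-related complications are separate endpoints; the procedure endpoint has no grade or cut-off

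*Protocol*

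**What the plan says.** Section 12.5 lists "Device-related complications" and "Procedure-related complications" as separate safety endpoints. Section 12.4 lists the same two items among the secondary objectives.

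Section 14.6 tells the investigator how to judge causality and says the assessment goes into the eCRF and, for serious events, the SAE form. It introduces the scale with: "The investigator will use the following definitions to assess the relationship of the adverse event to the use of study drug". Five grades follow: unrelated, unlikely, possible, probable, definite. Each grade names several possible causes together; for *possible* the text is "The Adverse Event may be related to the investigational agent, disease, concomitant medication, or other contributing cause". The section then counts *probable* and *possible* as related and *unlikely* as not related. It assigns neither *definite* nor *unrelated*.

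Section 16.3 sets out what the medical record must contain, including: "All adverse events: diagnosis, symptoms, onset date, severity, device and procedure relationship, action taken, outcome".

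Section 14.1 defines an adverse device effect as an adverse event related to use of the investigational device. It notes that adverse events include those related to the procedures involved, but it defines no matching procedure-related class.

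**The concern.** Two endpoints need two attributions, and the causality section provides for one. Its target is a study drug, in a trial whose product is a laser catheter, so a site must decide whether that means the catheter, the laser treatment or the whole session.

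This is likely to come up often. Section 10.2 describes ELCA as typically used before or together with balloon dilatation and/or stenting. Procedural success in 12.5 is judged after laser and adjunctive therapy. Section 11 lists access-site bleeding and complications of stenting or PTCA among the expected risks. An access-site bleed or a dissection from the adjunctive balloon belongs to the procedure but not obviously to the catheter.

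At stake is whether up to five sites count two safety endpoints by the same rule, in an open-label study with no comparator to absorb differences in attribution. The analysis plan cannot repair this later, because attribution is the investigator's judgment at the time of the event.

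**Working it through.** The point is mainly one of text, so the first step sets the sections side by side.

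| Element needed to count the endpoint | Device-related | Procedure-related |
|---|---|---|
| Listed as an outcome (12.4, 12.5) | yes | yes |
| Required in source for every AE (16.3) | yes | yes |
| Own event class (14.1) | yes, adverse device effect | no |
| Named as target of the 14.6 scale | no, only the study drug | no |
| Own related/not-related cut-off | only if study drug is read as device | no |

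The procedure column lacks a class, a scale and a cut-off. The device column lacks only an explicit target.

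**Does 16.3 fill the gap?** Its link to the CRF is "For data documented in the CRF respective source data in the medical record (source document) must be available". That runs from CRF to source: whatever is in the CRF needs a source entry. It does not say that every source item goes into the CRF. Nor does 16.3 give a scale or threshold for the procedure relationship.

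**How two sites could diverge under 14.6.** Take a dissection from the adjunctive balloon.
1. Site A reads study drug as the laser catheter, grades *unlikely*, and the event is not related.
2. Site B reads it as the study treatment session, grades *probable*, and the event is related.
3. Neither grade says whether the event is procedure-related.

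**Do the grades help?** They point the other way. Because each grade pools the investigational agent with disease, concomitant medication and other causes, a related rating does not by itself identify the device. The mapping covers three of five grades, so an event graded *definite*, the clearest case, has no stated place in the related count.

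**Size.** The plan's sample size reproduces: 25 patients required + 5 dropouts = 30 (section 15). If *k* patients are attributed differently, a proportion shifts by *k*/30:
- *k* = 1: 1/30 = 3.3 points
- *k* = 2: 2/30 = 6.7 points
- *k* = 4: 4/30 = 13.3 points

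If all five allowed dropouts occurred, the denominator would be 25 and one patient would count 1/25 = 4.0 points. The protocol gives no expected complication frequency, so the values of *k* are assumptions that show the range; they are not forecasts.

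**The case against.** A reader might infer that neither complication rate can be derived, or that the procedure-related rate cannot be computed. The document does not support that. Section 16.3 makes both relationships mandatory in source for all adverse events, and section 16.2 requires full source verification for endpoints, AEs and SAEs. Sections 14.1 and 14.2 give a device-related class that exists independently of the 14.6 scale. Section 13.12 requires an event form when a patient seeks advice between visits for complications attributable to the study procedure. Section 14.6 itself asks for another cause when a serious event is graded possible, probable or unrelated, and the procedure could be named there.

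It is also fair to say that:
- the limit to one rating per event is inferred from the single scale and single target, and is not stated;
- the eCRF, the SAE form and the safety management plan are not shown, and may already separate the two;
- 12.5 neither ties these endpoints to the 14.6 grade nor specifies a rate, and derivation rules are commonly left to the analysis plan.

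All of this stands, and it limits the point. It does not remove it. A source entry without a scale or threshold is not a consistently defined endpoint, and verification can only check what was recorded. The 13.12 form covers one situation, and the alternative-cause request covers only some grades of serious events. An analysis plan can choose a cut-off, but it cannot supply a graded procedure rating that was never requested. If the eCRF already has two fields, the protocol text still has to agree with it.

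**Conclusion.** The point holds as an inconsistency to be reconciled. Section 14.6 supplies one scale and one cut-off for one target, while 12.4, 12.5 and 16.3 call for two attributions. The device-related endpoint is partly protected by the adverse device effect definition. The procedure-related endpoint has no graded rating and no threshold, so its count may depend on each site's reading.

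Each patient attributed differently is worth 3.3 percentage points at 30 patients. How many would be affected cannot be judged from the protocol. The conclusion assumes that sites follow 14.6 as it stands and that the unseen forms do not already resolve the matter. It does not follow that the rates will be wrong or will differ by site, only that nothing in 14.6 prevents it. Device success, procedural success, MACE and the sample size are unaffected. This should be corrected, but it does not undermine the study.

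**What to change.** In section 14.6:

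1. Replace the reference to a study drug, and require two ratings in the eCRF and SAE form for every AE and SAE: (a) relationship to the ELCA catheter and laser; (b) relationship to the index procedure, including adjunctive therapy.
2. Reword the five grades so that each refers only to the target being rated, without pooling it with disease, concomitant medication or other causes.
3. Assign all five grades, including *definite* and *unrelated*, to related or not related. Applying the present scale twice without this step would carry its gaps into both counts.
4. State that device-related complications are counted from (a) and procedure-related complications from (b), and that one event may count in both.

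The cost is protocol wording and at most one extra field on the AE and SAE forms; none if the forms already hold both. Sites take on no new source documentation, because 16.3 already requires both relationships. No treatment or visit changes.

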14.1 ADVERSE EVENT DEFINITION AND CLASSIFICATION

Adverse Events are defined and classified in this section according to the current version of ISO 14155.

[figure not shown]

Figure 4 – Adverse event definition and classification

Adapted from ISO 14155

Spectranetics Corporation

Study Protocol Number: ELCA-1016

Version 1.0

Dated: 12 Oct 2016

AE – Adverse event:

Any untoward medical occurrence, unintended disease or injury, or untoward clinical signs (including abnormal laboratory findings) in subjects, users or other persons, whether or not related to the investigational medical device.

Note: This definition includes events related to the investigational medical device

Note: This definition includes events related to the procedures involved

Note: For users or other persons, this definition is restricted to events related to investigational medical devices

ADE – Adverse Device Effect:

An *adverse event* related to the use of an investigational medical device.

Note: This definition includes adverse events resulting from insufficient or inadequate instructions for use, deployment, implantation, installation, or operation, or any malfunction of the investigational medical device.

Note: This definition includes any event resulting from use error or from intentional misuse of the investigational medical device.

SAE – Serious Adverse Event:

An *adverse event* that

- a) led to death,
- b) led to serious deterioration in the health of the subjects, that either resulted in
 - 1) a life-threatening illness or injury, or
 - 2) a permanent impairment of a body structure or a body function, or
 - 3) in-subject or prolonged hospitalization, or
 - 4) medical or surgical intervention to prevent life-threatening illness or injury or permanent impairment to a body structure or a body function,
- c) led to foetal distress, foetal death or a congenital abnormality or birth defect

Note: Planned hospitalization for a pre-existing condition, or a procedure required by the CIP, without serious deterioration in health, is not considered a serious adverse event.

SADE – Serious Adverse Device Effect:

An *adverse device effect* that has resulted in any of the consequences characteristic of a serious adverse event.

USADE – Unanticipated Serious Adverse Device Effect:

Serious adverse device effect which by its nature, incidence, severity or outcome has not been identified in the current version of the risk analysis report.

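### The causality grades in 14.6 pool the device with every other cause, and the related/not-related rule omits Definite and Unrelated

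*Protocol*

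**What the plan says.** Everything turns on Protocol section 14.6.

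- **Purpose of the scale.** The lead-in reads: "The investigator will use the following definitions to assess the relationship of the adverse event to the use of study drug". The paragraph above it lists concomitant medication and disease among the confounders the investigator should weigh.
- **The grades.** There are five: Unrelated, Unlikely, Possible, Probable and Definite. Definite is "The Adverse Event is clearly related to the investigational agent, disease, concomitant medication, or other contributing cause". Unrelated is "The Adverse Event is clearly not related to the investigational agent, disease, concomitant medication, or other contributing cause". The three grades between them keep the same list of causes and change only the strength of the link.
- **The grouping rule.** For related, "events meeting the categories of probable or possible will be considered" is the operative wording. Unlikely is counted as not related. The rule names no other grade.
- **Alternative cause for SAEs.** When an opinion of "possible, probable, or unrelated to study drug is given, another cause of event must be provided by the investigator".
- **Recording.** "Assessment of causal relationship should be recorded in the eCRFs and in SAE form" (the latter for SAEs).

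Elsewhere, 14.1 defines an adverse device effect as an adverse event "related to the use of an investigational medical device". Section 16.3 requires the source record of each adverse event to show, among other items, "severity, device and procedure relationship, action taken, outcome". Sections 12.4 and 12.5 list device-related and procedure-related complications as secondary objectives and under the safety endpoint.

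**The concern.** A causality scale has to fix what the event is being related to. Here the lead-in fixes it as the study product, called a drug although the trial studies a device. The grades fix it as the product or any of three competing explanations. Those explanations should argue against attribution to the device; in the grade wording they count towards it.

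The grouping rule then leaves out the two ends of the scale, where the investigator is most certain. The procedure has no grade, although 12.4 and 12.5 ask for procedure-related complications and 16.3 expects a procedure relationship.

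The classification of device-related and procedure-related complications is at stake, as is adverse device effect status, in a single-arm study of up to 30 patients. With no control arm to help separate device effects from disease, attribution rests on the investigator's grade. One reclassified patient would be 1/30 = 3.3 percentage points. That figure only shows scale and does not predict that any patient will be misclassified.

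**Working it through.** No statistical formula applies. The check sets the statements of 14.6 side by side.

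**Step 1: each grade against the two rules that use it**

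| Grade | Strength of link | Causes pooled | Related/not-related rule | Another cause required (SAE) |
|---|---|---|---|---|
| 1 Unrelated | clearly none | all four | not assigned | yes |
| 2 Unlikely | doubtful | all four | not related | no |
| 3 Possible | may be | all four | related | yes |
| 4 Probable | likely | all four | related | yes |
| 5 Definite | clear | all four | not assigned | no |

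The four pooled causes are the product, disease, concomitant medication and any other contributing cause.

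- Grades that pool the four causes: 5 of 5.
- Grades that name the procedure: 0 of 5.
- Grades the rule assigns: 3 of 5. Unassigned: 5 − 3 = 2 (Definite and Unrelated).

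**Step 2: the same event under the two readings.** Take four events, each with one certain cause.

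| True sole cause | Grade wording | Lead-in | Difference |
|---|---|---|---|
| Device | 5 | 5 | 0 |
| Disease | 5 | 1 | 4 |
| Medication | 5 | 1 | 4 |
| Other | 5 | 1 | 4 |

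The readings disagree in 3 of 4 cases. Each disagreement is 5 − 1 = 4 steps, the full length of a five-grade scale. Under either reading all four events receive grade 1 or grade 5, which the grouping rule does not assign.

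**Step 3: does completing the rule by inference settle it?** Counting Definite as related and Unrelated as not related is the obvious intention. If the grades are applied as printed, however, an event due to disease alone is Definite and would then count as related. Completing the rule without rewording the grades therefore carries the first fault into the two-way split.

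**Step 4: the alternative-cause sentence.** An SAE graded Unrelated must be given another cause, although the definition of Unrelated excludes any other contributing cause. An SAE graded Unlikely, which the rule counts as not related, needs none. Leaving out Definite is logical.

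**Step 5: what relies on attribution.** Two of four secondary objectives (12.4) and two of five listed safety endpoints (12.5) depend on it. So do the device-effect definitions in 14.1, prompt reporting of non-serious device-related events in 14.2, and the review of related events in 17.7. No other causality scale appears in the protocol text available for this review; the classification figure in 14.1 was not reproduced.

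**The case against.** The strongest reply is that few investigators would read the grades literally. The lead-in, the reference to confounders and the alternative-cause sentence all point to the study product. Asking for another cause when an event is Unrelated makes sense only if that grade means unrelated to the product. This is fair as evidence of intent, but it confirms that the five definitions say something other than what was meant. The definitions are what the investigator is told to use.

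Second, the sides for Definite and Unrelated are easy to infer, and with up to 30 patients regrouping is trivial if the grade is captured. That stands for the grouping rule taken alone. It does not help with pooling, because a single grade covering four causes cannot show which one was meant.

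Third, none of 12.4, 12.5, 14.1, 14.2 or 17.7 cites the 14.6 grouping, and a clearly device-related event meets the plain words of 14.2 and 17.7. Section 16.3 requires device and procedure relationship in source, and 16.2 requires full verification of adverse event source data. The adverse event form and the safety management plan are not shown and may already hold separate fields. All of this stands. It makes misclassification a risk rather than a stated consequence, and part of it could be recovered later.

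Fourth, the 3-of-4 count uses constructed cases. That is also true: it measures how far the two sentences diverge and says nothing about how often such events will occur.

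**Conclusion.** The concern holds and should be fixed. Section 14.6 contradicts itself about what its grades rate: 5 of 5 definitions pool the device with three competing explanations, against the section's own lead-in. The two-way rule leaves 2 of 5 grades unassigned, the alternative-cause sentence does not fit the grades, and the procedure is not rated.

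Confidence is high for the text. No effect on results is claimed. The protocol gives no frequency for such events, so neither the direction nor the size of any bias in the device-related or procedure-related complication rates can be stated. SAE reporting under 14.8 covers all SAEs whatever their cause and is unaffected, as are MACE, device success and procedural success. The conclusion assumes that sites grade from the protocol's definitions and that no unseen form or plan overrides them.

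**What to change.** In 14.6:

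1. Reword all five grades so that each rates relation to the study device only, and change the references to a study drug accordingly.
2. Apply the same five grades separately to the index procedure, in line with 16.3.
3. Treat disease, concomitant medication and other causes as alternative explanations, recorded beside the grade and not inside it.
4. State the grouping in full: Possible, Probable and Definite are related; Unlikely and Unrelated are not related.
5. Reconcile the alternative-cause sentence with the reworded grades, including Unlikely.

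The cost is protocol wording and, if the adverse event form does not already have it, one field for the second relationship. No extra patients or procedures are needed. The reported device-related rate could move in either direction.
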